14.4 Sample Size and Accrual Rate

The sample size for this single site pilot three-arm study is targeted at 12, 78 and 20 evaluable patients in Arm 1, Arm 2 and Arm 3, respectively. In order to allow for a small number of

CC Protocol Number: 14-C-0140
Abbreviated Title: DCFBC in prostate cancer
Version date: 10/27/2015
CIP #: 9622

nonevaluable patients, the accrual ceiling will be set at 125. Assuming the accrual rate is 5-6 patients per month, the total length of accrual period for this study will be about 24 months.

15 SAFETY REPORTING REQUIREMENTS/DATA AND SAFETY MONITORING PLAN for NCI IRB

15.1 Definitions

15.1.1 Suspected adverse reaction

Suspected adverse reaction means any adverse event for which there is a reasonable possibility that the drug caused the adverse event. For the purposes of IND safety reporting, 'reasonable possibility' means there is evidence to suggest a causal relationship between the drug and the adverse event. A suspected adverse reaction implies a lesser degree of certainty about causality than adverse reaction, which means any adverse event caused by a drug.

15.1.2 Unexpected adverse reaction

An adverse event or suspected adverse reaction is considered "unexpected" if it is not listed in the investigator brochure or is not listed at the specificity or severity that has been observed; or, if an investigator brochure is not required or available, is not consistent with the risk information described in the general investigational plan or elsewhere in the current application. "Unexpected" also refers to adverse events or suspected adverse reactions that are mentioned in the investigator brochure as occurring with a class of drugs or as anticipated from the pharmacological properties of the drug, but are not specifically mentioned as occurring with the particular drug under investigation.

15.1.3 Serious

An Unanticipated Problem or Protocol Deviation is serious if it meets the definition of a Serious Adverse Event or if it compromises the safety, welfare or rights of subjects or others.

15.1.4 Serious Adverse Event

An adverse event or suspected adverse reaction is considered serious if in the view of the investigator or the sponsor, it results in any of the following:

- Death,
- A life-threatening adverse drug experience
- Inpatient hospitalization or prolongation of existing hospitalization
- Persistent or significant incapacity or substantial disruption of the ability to conduct normal life functions
- A congenital anomaly/birth defect.
- Important medical events that may not result in death, be life-threatening, or require hospitalization may be considered a serious adverse drug experience when, based upon appropriate medical judgment, they may jeopardize the patient or subject and may require medical or surgical intervention to prevent one of the outcomes listed in this definition.

CC Protocol Number: 14-C-0140
Abbreviated Title: DCFBC in prostate cancer
Version date: 10/27/2015
CIP #: 9622
15.1.5 Disability

A substantial disruption of a person's ability to conduct normal life functions.

15.1.6 Life-threatening adverse drug experience

Any adverse event or suspected adverse reaction that places the patient or subject, in the view of the investigator or sponsor, at immediate risk of death from the reaction as it occurred, i.e., it does not include a reaction that had it occurred in a more severe form, might have caused death.

15.1.7 Protocol Deviation (NIH Definition)

Any change, divergence, or departure from the IRB-approved research protocol.

15.1.8 Non-compliance (NIH Definition)

The failure to comply with applicable NIH Human Research Protections Program (HRPP) policies, IRB requirements, or regulatory requirements for the protection of human research subjects.

15.1.9 Unanticipated Problem

Any incident, experience, or outcome that:

- Is unexpected in terms of nature, severity, or frequency in relation to
 - (a) the research risks that are described in the IRB-approved research protocol and informed consent document; Investigator's Brochure or other study documents, and
 - (b) the characteristics of the subject population being studied; **AND**
- Is related or possibly related to participation in the research; **AND**
- Suggests that the research places subjects or others at a *greater risk of harm* (including physical, psychological, economic, or social harm) than was previously known or recognized.

15.2 NCI-IRB Reporting

15.2.1 NCI-IRB Expedited Reporting of Unanticipated Problems and Deaths

The Protocol PI will report to the NCI-IRB:

- All deaths, except deaths due to progressive disease
- All Protocol Deviations
- All Unanticipated Problems
- All serious non-compliance

Reports must be received by the NCI-IRB within 7 working days of PI awareness via iRIS.

15.3 NCI-IRB Requirements for PI Reporting at Continuing Review

The protocol PI will report to the NCI-IRB:

CC Protocol Number: 14-C-0140
Abbreviated Title: DCFBC in prostate cancer
Version date: 10/27/2015
CIP #: 9622

1. A summary of all protocol deviations in a tabular format to include the date the deviation occurred, a brief description of the deviation and any corrective action.
2. A summary of any instances of non-compliance
3. A tabular summary of the following adverse events:
 - All Grade 2 **unexpected** events that are possibly, probably or definitely related to the research;
 - All Grade 3 and 4 events that are possibly, probably or definitely related to the research;
 - All Grade 5 events regardless of attribution;
 - All Serious Events regardless of attribution.

NOTE: Grade 1 events are not required to be reported.

15.3.1 NCI-IRB Reporting of IND Safety Reports

Only IND Safety Reports that meet the definition of an unanticipated problem will need to be reported to the NCI IRB.

15.4 Data and Safety Monitoring Plan

15.4.1 Principal Investigator/Research Team

The principal investigator or appropriate designee and research nurse will monitor the study for AEs.

This study will not have a formal data safety monitoring plan (DSMP), however, the principal investigator and Lead Associate Investigator will re-evaluate the protocol after each patient.

The principal investigator reserves the right to terminate the study on safety grounds. If 3 study subjects experience \geq grade 2 ^{18}F DCFBC –possibly or definitely related SAEs then the study will be terminated. Before terminating the study, the investigator will ensure that a review of the overall risk/benefit analysis confirms the balance to be no longer acceptable. Should termination be necessary, the PI will arrange the relevant procedures, which will include informing the IRB, and the FDA and other relevant local and national authorities. On termination of the study, the investigator will assure that adequate consideration is given to the protection of enrolled subjects' interests. Termination of the study will be considered in the event of significant safety findings occurring at any time during the performance of the study.

Adverse events will be reported as required above. Any safety concerns, new information that might affect either the ethical and or scientific conduct of the trial, or protocol deviations will be immediately reported to the IRB using iRIS.

The principal investigator will review adverse event and response data on each patient to ensure safety and data accuracy. The principal investigator will personally conduct or supervise the investigation and provide appropriate delegation of responsibilities to other members of the research staff.

CC Protocol Number: 14-C-0140
Abbreviated Title: DCFBC in prostate cancer
Version date: 10/27/2015
CIP #: 9622

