6.1.1.1 Adverse Event Characteristics

- **CTCAE term (AE description) and grade:** The descriptions and grading scales found in the revised NCI Common Terminology Criteria for Adverse Events (CTCAE) version 4.0 will be utilized for AE reporting. All appropriate treatment areas should have access to a copy of the CTCAE version 4.0. A copy of the CTCAE

CC Protocol Number: 14-C-0140
Abbreviated Title: DCFBC in prostate cancer
Version date: 10/27/2015
CIP #: 9622

version 4.0 can be downloaded from the CTEP web site
http://ctep.cancer.gov/protocolDevelopment/electronic_applications/ctc.htm.

- **For expedited reporting purposes only:**
 - AEs for the agent that are ***bold and italicized*** in the CAEPR should be reported through CTEP-AERS only if the grade is above the grade provided in the SPEER.
- **Attribution** of the AE:
 - Definite – The AE *is clearly related* to the study treatment.
 - Probable – The AE *is likely related* to the study treatment.
 - Possible – The AE *may be related* to the study treatment.
 - Unlikely – The AE *is doubtfully related* to the study treatment.
 - Unrelated – The AE *is clearly NOT related* to the study treatment.

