6.2.1 Expedited Reporting Guidelines

Use the NCI protocol number and the protocol-specific patient ID assigned during trial registration on all reports.

Note: A death on study requires both routine and expedited reporting regardless of causality, unless as noted below. Attribution to treatment or other cause must be provided.

Death due to progressive disease should be reported as **Grade 5 “Neoplasms benign, malignant and unspecified (incl cysts and polyps) - Other (Progressive Disease)”** under the system organ class (SOC) of the same name. Evidence that the death was a manifestation of underlying disease (*e.g.*, radiological changes suggesting tumor growth or progression: clinical deterioration associated with a disease process) should be submitted.

Phase 0 Studies: Expedited Reporting Requirements for Adverse Events that Occur on Studies under an IND/IDE within 30 Days of the Last Administration of the Investigational Agent/Intervention^{1,2}

FDA REPORTING REQUIREMENTS FOR SERIOUS ADVERSE EVENTS (21 CFR Part 312)
NOTE: Investigators **MUST** immediately report to the sponsor (NCI) **ANY** Serious Adverse Events, whether or not they are considered related to the investigational agent(s)/intervention (21 CFR 312.64)

CC Protocol Number: 14-C-0140
 Abbreviated Title: DCFBC in prostate cancer
 Version date: 10/27/2015
 CIP #: 9622

An adverse event is considered serious if it results in ANY of the following outcomes:
 
 1) Death 2) A life-threatening adverse event 3) An adverse event results in inpatient hospitalization or prolongation of existing hospitalization for \geq 24 hours 4) A persistent or significant incapacity or substantial disruption of the ability to conduct normal life functions 5) A congenital anomaly/birth defect. 6) Important Medical Events (IME) that may not result in death, be life threatening, or require hospitalization may be considered serious when, based upon medical judgment, they may jeopardize the patient or subject and may require medical or surgical intervention to prevent one of the outcomes listed in this definition (FDA, 21 CFR 312.32; ICH E2A and ICH E6). 	

ALL SERIOUS adverse events that meet the above criteria MUST be immediately reported to the NCI via CTEP-AERS within the timeframes detailed in the table below.
	
Grade 1 and 2 Timeframes	Grade 3-5 Timeframes
10 Calendar Days	24-Hour 5 Calendar Days

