12 DATA COLLECTION AND EVALUATION

12.1 Data Collection

12.1.1 Clinical Data

All data will be kept secure. Personal identifiers will not be used when collecting and storing data. An enrollment log will be maintained in the regulatory binder/file which is the only location of personal identifiers with unique subject identification number.

Clinical data including summary and demographic data will be collected and entered into NCI CCR Database, C3D. Adverse events occurring during any scanning session will be recorded. Adverse events which are designated possibly, probably or definitely related to ¹⁸F DCFBC will also be recorded.

Imaging data will include storage of the reconstructed images and image derived parameters on a secure, password protected lab imaging database. Images may also be stored in the clinical

CC Protocol Number: 14-C-0140
Abbreviated Title: DCFBC in prostate cancer
Version date: 10/27/2015
CIP #: 9622

center PACS. The lab imaging database will be stored and maintained in the Molecular Imaging Program facilities. Personal identifiers will not be used when storing data.

NCI Molecular Imaging Program may exchange anonymized clinical data with working groups, and qualified investigators. The anonymized image data will be stored in an existing secure off-site imaging database (EXEC PACS) and these images may be shared with researchers at other institutions.

During the one year follow-up period, the patient's PSA levels and prostate cancer related medical history, biopsy results, imaging studies and will be collected (reports and CD copies of the imaging studies).

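### The three-subject safety stopping rule leaves out probably related SAEs, so as written a weaker attribution counts and a stronger one does not

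*Combined protocol and SAP*

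**What the plan says.** Section 15.4.1 sets the rule: "If 3 study subjects experience" grade 2 or higher SAEs with the stated attribution to the agent, the study stops. The attribution clause is "possibly or definitely related SAEs then the study will be terminated". The next sentence makes termination conditional on a risk/benefit review that finds the balance no longer acceptable. The section also says that there is no formal data safety monitoring plan, that the principal investigator and lead associate investigator re-evaluate the protocol after every patient, and that the principal investigator may end the study on safety grounds.

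Section 6.1.1.1 defines five attribution levels: definite, probable, possible, unlikely and unrelated. Two of the definitions matter here: "Probable – The AE *is likely related* to the study treatment" and "Possible – The AE *may be related* to the study treatment".

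Two other sections list the levels that count as related, and both name three:

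- Section 12.1.1, on data to be recorded: "Adverse events which are designated possibly, probably or definitely related to" the agent.
- Section 15.3, on IRB continuing review: "All Grade 3 and 4 events that are possibly, probably or definitely related to the research". The item before it, on unexpected grade 2 events, uses the same three levels.

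**The concern.** The rule names the lowest and highest of the three related levels and skips the middle one. On the protocol's own scale, *probable* is a stronger judgement of causality than *possible*. A stopping rule should never give less weight to stronger evidence of harm, and this one does if it is applied as written.

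The setting makes the exact wording worth having. This is the only numeric safety threshold in the documents; the rules in section 14.3 concern futility. Section 6.1 says that no comprehensive adverse event list yet exists for the agent. The human toxicity data in section 2.2.1.2 come from five patients. Section 16.1 describes the study as more than minimal risk with no direct benefit expected, and accrual may reach 125 (section 4.1). With no formal monitoring plan, the one explicit count should not depend on the reader to supply a missing category.

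**Working it through.** **Levels counted, side by side**

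| Attribution level (section 6.1.1.1) | Recorded as related (12.1.1) | Grade 3 and 4 events reported as related (15.3) | Counts toward the three subjects (15.4.1, literal) |
|---|---|---|---|
| Definite | yes | yes | yes |
| Probable | yes | yes | **no** |
| Possible | yes | yes | yes |
| Unlikely | no | no | no |
| Unrelated | no | no | no |

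The rule therefore names 2 of the 3 levels that the protocol treats as related elsewhere. No other section extends the stopping rule to *probable* events.

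**Effect on the count**

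The unit is the subject. Take three subjects who each have at least one grade 2 or higher SAE that is possibly, probably or definitely related. Let k be the number whose only such SAE is rated *probable*.

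- Literal count = 3 − k
- Count with *probable* included = 3

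| k | Literal count | Literal rule met? | Count with *probable* | Corrected rule met? |
|---|---|---|---|---|
| 0 | 3 | yes | 3 | yes |
| 1 | 2 | no | 3 | yes |
| 2 | 1 | no | 3 | yes |
| 3 | 0 | no | 3 | yes |

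**Illustration only**

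The plan states no operating characteristics for this rule, so there is no figure to reproduce. To show how sensitive it could be, let X be the number of subjects who count toward the rule among N = 125 (the accrual ceiling). Treat subjects as independent, let p be the per-subject probability of a qualifying SAE that is at least possibly related, and let s be the share of affected subjects whose only such SAE is *probable*. Then:

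- Corrected rule: P(X ≥ 3) with X ~ Binomial(125, p)
- Literal rule: P(X ≥ 3) with X ~ Binomial(125, p(1 − s))

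| Assumed p | Corrected | Literal, s = 20% | Literal, s = 33% | Literal, s = 50% |
|---|---|---|---|---|
| 1% | 0.131 | 0.080 | 0.052 | 0.025 |
| 3% | 0.727 | 0.580 | 0.457 | 0.289 |
| 5% | 0.952 | 0.880 | 0.790 | 0.607 |

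Both p and s are assumptions. The documents give neither, and the conclusion does not depend on this table.

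**The case against.** The strongest reply is that the phrase is a range with its two ends named, and that nobody would count an SAE that may be related while refusing one that is likely related. The protocol uses similar shorthand elsewhere. The definition of an unanticipated problem in section 15.1.9 speaks of events that are related or possibly related, and a footnote in section 6.2.1 takes a possible attribution as a floor. This is good evidence of what was meant. It does not change what the rule says: it joins two defined categories with *or*, in the same chapter where section 15.3 lists all three.

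The second reply is that little hangs on the count:

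- Reaching three subjects leads to a risk/benefit review, not to automatic closure.
- Termination may be considered for significant safety findings at any time.
- Safety concerns go to the IRB immediately (section 15.4.1), and unanticipated problems within 7 working days (section 15.2.1).
- Under section 6.2.1 the sponsor is told at once of any SAE, "whether or not they are considered related to the investigational agent(s)/intervention".
- At continuing review the IRB receives "All Serious Events regardless of attribution".

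All of this stands, and it means that a probably related SAE would be seen and could be acted on. But reporting does not itself trigger termination, and the other stopping provisions are discretionary. The three-subject rule exists to force the question at a fixed point, and the literal wording can let that point pass.

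It is also fair to say that 3 − k only restates the omission, and that the five earlier patients had no severe adverse events and no event rated above unlikely to be related. No claim is made here about how often the gap would matter.

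**Conclusion.** The concern holds. As written, section 15.4.1 counts a weaker attribution and skips a stronger one, against the protocol's own scale and its own lists of related events. The rule fails to trigger at the third affected subject whenever at least one of the three has only a *probable* qualifying SAE.

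This rests on a literal reading; a reader who takes the phrase as a range would reach the intended count. The practical impact is limited by the reporting duties and the investigator's discretion. No estimate, sample size or analysis is affected. It should still be corrected, because a stated safety decision rule gives the wrong answer when followed.

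**What to change.** In section 15.4.1, insert *probably* so that the rule names the possible, probable and definite levels, as sections 12.1.1 and 15.3 do. Keep the threshold of three subjects, the grade 2 floor and the risk/benefit review before termination as they are. The cost is one word in an amendment, with no change to sample size, analysis or reporting duties.

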16 HUMAN SUBJECTS PROTECTION

16.1 Rationale for Subject Selection

The patient population in whom this disease occurs is adult males. All ethnic groups/ race categories would be represented as they are represented in the disease as a whole. Cognitively impaired individuals will not be included in this study if they are unable to understand the informed consent. Physically impaired persons who otherwise satisfy eligibility criteria will be included in this study. This study is considered more than minimal risk to subjects and no direct benefits to the patient are expected. We anticipate that a thorough discussion of the study at the time informed consent is obtained will minimize any susceptibility to undue influences and unnecessary risks to research subjects.

16.2 Participation of Children

Children will not be considered as research subjects for this study as this disease has never been documented to occur in children.

16.3 Evaluation of Benefits and Risks/Discomforts

Risks and discomforts of the experimental procedure are expected to be low and related to the risks of ^{18}F DCFBC, and PET/CT imaging. Most complications are expected to be minor and require no treatment.

Risks and discomforts associated with ^{18}F DCFBC PET/CT imaging are discomfort of an IV placement and the theoretical effects of the amount of additional radiation exposure. The maximum effective dose is 2.4 rem for Arm 1 and for Arm 2 and 5.9 rem for Arm 3, which exceeds the NIH Radiation Safety Committee's guidelines of 5.0 rem per year for adults. The benefits of the study for this group with metastatic cancer outweigh the potential radiation risks. The higher dosage for Arm 3 is due to the inclusion of F-Na PET/CT at baseline and follow-up. A follow-up ^{18}F DCFBC PET/CT image also accounts for Arm 3's higher dose. The activity of F18 FDCFB is 8 mCi and the activity of F18 NaF is 3 mCi. In this study, the subject will be required to lie still on his back for up to 45- minutes at a time, and this might produce some discomfort.

16.4 Risks/Benefits Analysis

The risks of participation are low based on the very low doses used and prior knowledge of a low rate of AEs for ^{18}F DCFBC. No direct benefits to the subject are anticipated; however, the knowledge derived from the study could have broader implications in the field. As the significance of a ^{18}F DCFBC-depicted lesion is uncertain, treatment decisions will not be based on ^{18}F DCFBC PET/CT findings. Further evaluation with standard of care diagnostic imaging and/or biopsy will be performed at the discretion of the referring physician. The decision to pursue further imaging or pathological confirmation and the methods of doing so will be left to the referring clinician and is not dictated by this imaging protocol.

CC Protocol Number: 14-C-0140
Abbreviated Title: DCFBC in prostate cancer
Version date: 10/27/2015
CIP #: 9622

18 APPENDICES

18.1 APPENDIX A: Performance Status Criteria

ECOG Performance Status Scale	
Grade	Descriptions
0	Normal activity. Fully active, able to carry on all pre-disease performance without restriction.
1	Symptoms, but ambulatory. Restricted in physically strenuous activity, but ambulatory and able to carry out work of a light or sedentary nature (e.g., light housework, office work).
2	In bed <50% of the time. Ambulatory and capable of all self-care, but unable to carry out any work activities. Up and about more than 50% of waking hours.
3	In bed >50% of the time. Capable of only limited self-care, confined to bed or chair more than 50% of waking hours.
4	100% bedridden. Completely disabled. Cannot carry on any self-care. Totally confined to bed or chair.
5	Dead.

CC Protocol Number: 14-C-0140
 Abbreviated Title: DCFBC in prostate cancer
 Version date: 10/27/2015
 CIP #: 9622

